7.5.4 SERIOUS ADVERSE EVENT REPORTING AND FOLLOW-UP

Any such experience due to any cause, which occurs during the course of the investigation or within 30 days of the last study visit, must be reported to the ATRI Coordinating Center within 24 hours after learning of the event. This in turn will trigger an alert to the appropriate ATRI Coordinating Center personnel, which will lead to the initiation of the creation of a report. Sites will report SAEs based on the IRB/IEC and local institutional requirements.

A serious adverse event (SAE) reported to have occurred within 24 hours of amyloid (FBP, FBB, NAV4694) or tau (FTP, MK6240, PI2620) PET tracer administration will be reported, regardless of the investigator's opinion of causation. Thereafter, sites must continue to report any serious or life-threatening adverse event whether or not it is related to study procedures. A subset of those SAEs may then be reported to Avid, Life Molecular Imaging (LMI) and Cerveau for events related to florbetaben, florbetapir, NAV4694, flortaucipir, MK6240, PI2620.

All available information, including the site PI's assessment of causality, must be provided at the time the initial SAE is reported via the eCRF. The initial SAE report is to be followed as soon as possible by detailed descriptions including copies of hospital case reports, autopsy reports, and other documentation requested by the Data and Coordinating Center and/or the IRB/IEC.

Any relevant follow-up information received on SAEs should be reported within 24 hours of its receipt. If the relevant follow-up information changes the site PI's assessment of causality, this should also be noted on the follow-up SAE form.

The site PI is responsible to notify their IRB/IEC of the occurrence of the SAE in writing, if required by their institution. A copy of this communication must be forwarded to the Data and Coordinating Center, the IRB/IEC, or delegate(s) to be filed in the TMF.

The detailed contact information for reporting of SAEs is on the Study Contact Sheet made available to all sites.

For urgent safety issues, please ensure all appropriate medical care is administered to the participant and contact the appropriate study team member listed on the Study Contact Sheet.

7.5.4.1 EXPEDITED REPORTING

The sponsor must inform site PIs (or as regionally required, the head of the medical institution) and regulatory authorities of reportable events, in compliance with applicable regulatory requirements, on an expedited basis (i.e., within specific time frames). For this reason, it is imperative that clinical sites provide complete SAE information in the manner described in this protocol and the relevant study manual.

7.5.5 EVENT CLASSIFICATION

37

Every effort must be made by the site PI (or medically qualified designee) to categorize each AE according to its severity and its relationship to the investigational PET tracer products.

7.5.5.1 SEVERITY

The site PI (or medically qualified designee) will assess adverse event (AE) severity using the protocol defined grading system described below and recorded in the CRF.

- Mild Discomfort noticed, but events require minimal or no treatment and do not interfere with the participant's daily activities.
- Moderate Discomfort sufficient to reduce or affect normal daily activity. Events result in a low level of inconvenience or concern with the therapeutic measures. Moderate events may cause some interference with functioning.
- Severe Events interrupt a participant's usual daily activity and may require systemic drug therapy or other treatment. Severe events are usually potentially life-threatening or incapacitating. Of note, the term "severe" does not necessarily equate to "serious".

7.5.5.2 RELATIONSHIP TO INVESTIGATIONAL PRODUCTS AND STUDY PROCEDURES

The site PI (or medically qualified designee) will assess the relationship of an adverse event (AE) to NAV4694, MK6240, and PI2620 and study participation/procedures based on temporal relationship and clinical judgment. The degree of certainty about causality will be graded using the categories below and recorded in the CRF.

- Definitely Related There is clear evidence to suggest a causal relationship, and other possible contributing factors can be
 ruled out. The clinical event, including an abnormal laboratory test result, occurs in a plausible time relationship to study
 intervention administration and cannot be explained by concurrent disease or other drugs or chemicals. The response to
 withdrawal of the study intervention (dechallenge) should be clinically plausible. The event must be pharmacologically or
 phenomenologically definitive, with use of a satisfactory rechallenge procedure if necessary.
- Probably Related There is evidence to suggest a causal relationship, and the influence of other factors is unlikely. The clinical event, including an abnormal laboratory test result, occurs within a reasonable time after administration of the study intervention, is unlikely to be attributed to concurrent disease or other drugs or chemicals, and follows a clinically reasonable response on withdrawal (dechallenge). Rechallenge information is not required to fulfill this definition.
- Possibly Related There is some evidence to suggest a causal relationship (e.g., the event occurred within a reasonable time after administration). However, other factors may have contributed to the event (e.g., the participant's clinical condition, other concomitant events). Although an AE may rate only as "possibly related" soon after discovery, it can be flagged as requiring more information and later be upgraded to "probably related" or "definitely related", as appropriate.
- Unlikely Related A clinical event, including an abnormal laboratory test result, whose temporal relationship to study intervention administration makes a causal relationship improbable (e.g., the event did not occur within a reasonable time after administration of the investigational PET tracer product) and in which other drugs or chemicals or underlying disease provides plausible explanations (e.g., the participant's clinical condition, other concomitant treatments).
- Not Related The event is completely independent of investigational product administration, and/or evidence exists that the event is definitely related to another etiology. There must be an alternative, definitive etiology documented by the clinician.

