2.3.1.1 STUDY PROCEDURES

2.3.1.1.1 Clinical, Cognitive, Neuropsychological Testing

Clinical, cognitive, and neuropsychological testing conducted in this study may cause some participants to become upset, frustrated, bored, or tired.

2.3.1.1.2 **Imaging**

Positron Emission Tomography (PET)

The primary risk related to PET imaging is that of radiation exposure associated with the injected radiotracers and accompanying CT (if a PET/CT scanner is used). There is also minor risk associated with the venipuncture, placement of an intravenous catheter, and radioisotope injection (pain and bruising or painful infiltration of a failed injection).

The following [18F] labeled radiotracers will be utilized for PET imaging in this study:

- Florbetaben (Neuraceq)
- Florbetapir (Amyvid)
- NAV-4694 (Flutafuranol)
- Flortaucipir (AV-1451, T807)
- MK-6240
- PI-2620

Information about safety and risk can be found in respective Investigator Brochures and/or Package Inserts.

The radiation doses for each PET scan are not themselves expected to produce any harmful effects, although there is no known minimum level of radiation exposure considered to be totally free of the risk of causing genetic defects or cancer. The risk associated with the amount of radiation exposure participants receive in this study is considered low and comparable to everyday risks. If a female is not surgically sterile or post-menopausal by two years, a pregnancy test will be performed. Participants with positive pregnancy test will be ineligible for PET imaging.

More information about the known and expected benefits, risks, and reasonably anticipated adverse events (AEs) of these tracers can be found in their corresponding Investigator's Brochures or package inserts.

Radiation exposure from all 6 radiotracers in ADNI can be found in relevant study manuals.

Other risks associated with PET scanning include fatigue and discomfort at having to remain in the scanner for up to 30 minutes, and the discomfort and possible bruising associated with intravenous injections. The lowest possible dose of radioactivity compatible with good image quality is used. All IV catheters are placed by medical professionals with extensive training and experience. Experimenters and subjects can communicate via intercom during the scan.

All participants in this study will receive one amyloid PET scan (either FBP, FBB, or NAV4694), and one tau PET scan (either FTP, MK6240, or PI2620) every other year.

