7.3.1.2 DATA ACQUISITION FOR PET SCANS

All ADNI participants will complete one amyloid PET scan and one tau PET scan every two years. Scans must be completed within 2 weeks before or 2 weeks after the in-clinic assessments at Initial/Baseline visit and at two-year intervals.

Individuals who are retained in ADNI4 from ADNI3 will continue to have amyloid PET scans with the ligand that was used in ADNI3 (either FBB or FBP) and will continue to have tau PET scans with the ligand that was used in ADNI3 (FTP). Participants that are newly recruited to ADNI4 will be assigned to tracers based on the clinical site proximity to PET tracer manufacturing sites. In ADNI4 because there are 3 possible amyloid tracers and 3 possible tau tracers, there are 9 possible combinations of tracers that new individuals will receive. Each participant will be assigned to one amyloid tracer and one tau tracer that is expected to remain stable for the duration of the study. In the United States, florbetapir, florbetaben and flortaucipir are all FDA approved tracers for PET imaging. NAV4694, MK6240, and PI2620 are not currently FDA approved and will be used under IND held by ATRI investigators. In Canada, only florbetaben is approved by Health Canada (HC) for PET imaging. Use of remaining tracers (florbetapir, flortaucipir, NAV4694, MK6240, and PI2620) will be submitted to HC by ATRI investigators for approval for use in the ADNI4 study.

Scan protocols differ for each tracer. The injected doses for each tracer are listed in the table to the right. After insertion of an intravenous line, tracer is injected outside the scanner. Following injection, participants remain in a comfortable state, usually in a chair but not in the scanner, for a period of time. Imaging times after injection are listed in the table for each tracer. Prior to each scan an x-ray CT (for PET/CT systems), or positron transmission scan (for PET-only systems) is obtained for attenuation correction of the image; an MRI scan (for PET/MRI systems) may be obtained before, after or during the PET scan. Technical details for scan acquisition will be provided in a technical manual and radiation dose exposure is provided in the technical manual. The total time commitment for a PET scan may range from about 1.5 hours to 2.5 hours.

Tracer	Injected Dose	Imaging Time (post-injection)
Florbetapir	10 mCi	50-70 min
Florbetaben	8.1 mCi	90-110 min
NAV4694	8.1 mCi	50-70 min
Flortaucipir	10 mCi	75-105 min
MK6240	5 mCi	90-110 min

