7.5 ADVERSE EVENTS AND SERIOUS ADVERSE EVENTS FOR IN-CLINIC COHORT

7.5.1 ADVERSE EVENT (AE) DEFINITION

An Adverse Event (AE) is any untoward medical occurrence including adverse change from the participant's baseline condition, including clinical or laboratory tests, or abnormalities that occur during the course of the study after consent.

All AEs are to be documented, regardless of relationship to study procedures, commercial, or investigational products used in this study (amyloid (Florbetapir, Florbetaben, NAV4694) or tau (Flortaucipir, MK6240, PI2620) PET tracers), beginning from the time the participant signs the Informed Consent Form (ICF) through the last study visit or last assessment.

All research team members will be participating in ensuring subject safety. All participants will be evaluated for adverse events at each visit.

The investigator is obliged to follow participants with AE's until the events have subsided, the conditions are considered medically stable, or the participants are no longer available for follow up. Participants who discontinue due to Adverse Events will be treated and followed according to established medical practice. All pertinent information will be entered into the eCRF.

AEs the site PI (or medically qualified designee) deems related to study procedures or investigational products used in this study and serious adverse events (SAEs) occurring within 24 hours of PET tracer administration, regardless of causality, are to be documented beginning from the time the participant signs the ICF through the last study visit or last assessment.

AE identification criteria and reporting requirements will be provided in the relevant study manual and must be followed regardless of applicable regulatory requirements that may be less stringent.

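### AE relatedness is graded by tracer for only three of the six PET tracers, and section 7.5.1 states its AE capture rule twice in terms that do not match

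*Protocol*

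**What the plan says.** **Tracers in use.** The imaging part of section 2.3.1.1 lists six tracers: "Radiation exposure from all 6 radiotracers in ADNI can be found in relevant study manuals". Three are for amyloid (florbetapir, florbetaben, NAV4694) and three for tau (flortaucipir, MK6240, PI2620).

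**Relatedness grade.** Section 7.5.5 asks for each AE to be classified by severity and by relationship to the investigational tracer products. Section 7.5.5.2 then names what is graded: the site PI or designee "will assess the relationship of an adverse event (AE) to NAV4694, MK6240, and PI2620 and study participation/procedures".

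**Who gets which tracer.** Section 7.3.1.2: "Individuals who are retained in ADNI4 from ADNI3 will continue to have amyloid PET scans with the ligand that was used in ADNI3", which it gives as florbetaben or florbetapir, with flortaucipir as the continuing tau tracer. New participants are assigned by the site's proximity to a manufacturer. On approval, florbetapir, florbetaben and flortaucipir are FDA approved and the other three are used under IND. For the other country, "In Canada, only florbetaben is approved by Health Canada (HC) for PET imaging", and the remaining five are to be submitted to Health Canada.

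**Capture of AEs.** Section 7.5.1, second paragraph: "All AEs are to be documented, regardless of relationship to study procedures, commercial, or investigational products used in this study", from consent to the last visit or assessment. Its fifth paragraph covers the same period but describes a smaller set, namely AEs that the PI "deems related to study procedures or investigational products used in this study and serious adverse events (SAEs) occurring within 24 hours of PET tracer administration".

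**SAEs.** Section 7.5.4 covers any SAE "which occurs during the course of the investigation or within 30 days of the last study visit". It requires the PI's causality assessment with the initial report and provides that some SAEs related to any of the six tracers may be passed to the suppliers.

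**The concern.** The list in section 7.5.5.2 coincides with the tracers that lack FDA approval. The study also runs in Canada, where two of the unlisted tracers lack approval too, and other sections refer to relatedness without that limit. If the CRF is built from section 7.5.5.2, a non-serious AE after florbetapir, florbetaben or flortaucipir will carry a grade for study participation and procedures but none for the tracer. That shared category also covers venipuncture, MRI and lumbar puncture, so a suspected tracer effect cannot be told apart later without going back to source records.

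The two paragraphs of section 7.5.1 raise a different problem. A 24-hour clause that applies whatever the cause has a function only if other unrelated events are not captured. A site could therefore take the fifth paragraph as the operative limit and leave out unrelated non-serious AEs that the second paragraph requires.

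**Working it through.** The protocol gives no figure to reproduce here. The check is a comparison of lists and a count.

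**Step 1: tracers used against tracers graded.**

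| Tracer | Target | Named in 7.5.5.2 | FDA approved (7.3.1.2) | Approved in Canada (7.3.1.2) | Kept by ADNI3 participants (7.3.1.2) | In 7.5.4 forwarding list |
|---|---|---|---|---|---|---|
| Florbetapir | amyloid | no | yes | no | yes | yes |
| Florbetaben | amyloid | no | yes | yes | yes | yes |
| NAV4694 | amyloid | yes | no | no | no | yes |
| Flortaucipir | tau | no | yes | no | yes | yes |
| MK6240 | tau | yes | no | no | no | yes |
| PI2620 | tau | yes | no | no | no | yes |

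- Named for a grade: 3 of 6. The named set equals the set not FDA approved.
- ADNI3 tracers named: 0 of 3.
- Unapproved in Canada: 5. Of these, 3 are named and 5 − 3 = 2 are not (florbetapir, flortaucipir).

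**Step 2: tracer pairs for new participants.** There are 3 amyloid × 3 tau = 9 pairs, as section 7.3.1.2 also states.

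- Both tracers unlisted: 2 × 1 = 2 (florbetapir or florbetaben, with flortaucipir).
- Both listed: 1 × 2 = 2 (NAV4694 with MK6240 or PI2620).
- One of each: 9 − 2 − 2 = 5.

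In those five mixed pairs an AE is graded against one of the participant's tracers and not the other. Section 7.3.1 lets the two scans be as little as 12 hours apart. These are counts of pairs, not of people, since the protocol gives no distribution across pairs.

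**Step 3: participants.** Section 4.1.1 allows up to 750 rollovers of up to 1,500, so at most 750/1,500 = 50% receive only unlisted tracers by the rollover route. The true number may be lower. Section 7.3.1.2 fixes tracers only for those retained from ADNI3, section 5.1.1.2 also admits people followed in ADNIGO or ADNI2, and section 7.1.6.1 lets rollovers choose telephone visits on entry.

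**Step 4: the capture rules side by side.**

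| Place | What is captured |
|---|---|
| 7.5.1, second paragraph | all AEs, related or not |
| 7.5.1, fifth paragraph | related AEs, plus SAEs within 24 hours of tracer whatever the cause |
| 7.5.3 | all AEs and SAEs, related or not |
| 7.5.4 | every SAE, related or not, including after the 24 hours |
| 9.5 | all AEs recorded in the EDC system |

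The fifth paragraph's set lies inside the second's, and it contains no word such as only. A site that follows the second paragraph therefore satisfies both. Sections 7.5.3 and 9.5 repeat the broad rule for AEs, and 7.5.4 does so for SAEs.

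**Step 5: end of collection.** Sections 7.5.1 and 7.5.3 stop at the last visit or assessment, and 7.5.3 names SAEs in that window. Section 7.5.4 runs SAEs for 30 days beyond the last visit. A site can comply with both by adding the 30-day tail for SAEs.

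**The case against.** The strongest reply is that section 7.5.5.2 also grades every AE against study participation and procedures. The protocol treats PET as a study procedure: section 2.3.1.1 covers PET, including the injection, under that title, and section 7.1.1 ranks both PET scans among the procedures. A reader might infer that the three unlisted tracers have no causality grade at all. That goes too far, because what is missing is a grade specific to the tracer.

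A reader might also infer that related reactions to those tracers could not be found for expedited reporting, or that SAEs more than 24 hours after a scan would be lost. Section 7.5.4 answers both. The PI's causality assessment accompanies every initial SAE report, SAEs within 24 hours of any of the six tracers are reported whatever the PI thinks of causation, and later SAEs must still be reported whether related or not.

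A further inference would be that tracer event rates are confounded with how sites read section 7.5.1. That needs sites to take the narrow reading against four statements of a broader rule. In addition, no aim in section 3 or analysis goal in section 8.2 compares AE rates between tracers.

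Finally, the three-tracer list has a visible rationale in US IND status. That stands for US sites. It does not explain the list at Canadian sites, nor does it fit the all-tracer wording of section 7.5.4.

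**Conclusion.** The point holds as a conflict in the safety text with a limited consequence. Followed as written, section 7.5.5.2 gives no tracer-specific relatedness grade for florbetapir, florbetaben or flortaucipir, and the loss falls mainly on non-serious AEs. It affects at most 750 rollovers, plus new participants on 2 of the 9 tracer pairs in full and 5 of the 9 in part. At Canadian sites, 2 of the 5 unapproved tracers are left out of the list.

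The two capture paragraphs of section 7.5.1 are a drafting fault. The second is redundant under the first and open to misreading, but the rest of the protocol supports the broad rule. The differing end dates are minor, since both can be met.

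This rests on the CRF following section 7.5.5.2 literally. The study manual, which section 7.5.1 cites for reporting details, is not at hand and may already record more.

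**What to change.** 1. In section 7.5.5.2, record the relatedness grade against the tracer actually administered, for all six tracers, and keep the separate grade for study participation and procedures. Align sections 7.5.5 and 7.3.1.2 so that the meaning of investigational product is clear in both countries.
2. Reconcile the second and fifth paragraphs of section 7.5.1 with sections 7.5.3, 7.5.4 and 9.5 into one capture rule.
3. As a minor point, state in sections 7.5.1 and 7.5.3 that SAEs are also reported up to 30 days after the last visit, as section 7.5.4 has it, or otherwise reconcile the two.

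The cost is protocol wording, one CRF field and a few more causality assessments. It is better done before sites accumulate AE records, because a tracer-specific judgement is hard to reconstruct afterwards.

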1.1 SYNOPSIS

6

Title:	Alzheimer's Disease Neuroimaging Initiative 4 (ADNI4): In-Clinic Cohort		
Study Description:	Non-randomized, natural history, non-treatment study		
Objectives:	 Primary Objectives: Validation of biomarker measures Inform clinical trial design Increased inclusion of underrepresented populations (URPs) to improve generalizability of results and advance our understanding of health disparities across URPs. Utility of web-based cognitive testing and blood-based biomarkers to remotely identify and monitor those with AD biomarker pathology Longitudinal changes in cognition and associated biomarkers Prediction of cognitive decline Discovery of novel risk and protective genes and pathways, and other known disease proteins found in AD brains. 		
Study Population:	Men and women aged 55-90 years across Cognitively Normal (CN), Mild Cognitive Impairment (MCI), and Dementia (DEM) populations. • Up to 750 new participants will be enrolled into the in-clinic cohort. Up to 750 will be rollover participants from ADNI3.		
Phase:	N/A		
Descriptions of Sites/Facilities Enrolling Participants:	Approximately 65 sites across the United States and Canada		
Description of Study Intervention:	: N/A		
Study Duration:	5 years		
Participant Duration:	The participant journey from initial visit to final visit may last up to 5 years		

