Magnetic Resonance Imaging (MRI)

There are no proven biological risks associated with MRI scanning. All participants will be screened for medical contraindications for MRI, which include metallic foreign bodies in the brain or eye, or cardiac pacemakers. However, there is a slight risk that a participant may accidentally bring metal into the MR scanner room, which could be pulled into the MRI magnet and injure the participant.

There is a slight risk of anxiety due to claustrophobia and noise. If a participant experiences anxiety when placed into the MR scanner, the participant may be removed from the scanner and offered the option of continuing or terminating the MRI and/or the study.

2.3.1.1.3 **Biospecimens**

Blood Draw

15

The risks of blood draw include pain from the needle, bruising or infection at the site of the venipuncture, or fainting as a response to blood draw.

v1.0

Lumbar Puncture

Lumbar puncture (LP) may be associated with pain during the performance of the procedure. This is usually temporary and confined to the lower back. Headache may occur in some elderly people who undergo LP. Less commonly, a persistent low-pressure headache may develop, probably due to leakage of CSF. Lower rates of post-LP headache have been noted in elderly patients, and when atraumatic (Sprotte) needles are used. If a post-LP headache persists, it may need additional treatment (e.g. additional fluids and analgesics). Uncommonly a blood patch (injection of some of the participant's blood to patch the CSF leak) may be needed. Potential but rare risks of LP include infection, damage to nerves in the back, and bleeding into the CSF space. In an effort to mitigate these risks, an experienced clinician must perform the LP.

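### The dechallenge wording in Section 7.5.5.2 does not fit one-off tracer injections and procedures: read literally it blocks Probably Related, and it leaves Definitely Related ambiguous

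*Protocol*

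**What the plan says.** Protocol Section 7.5.5.2 sets a five-level causality scale, from *Definitely Related* to *Not Related*. It applies to the three investigational tracers (NAV4694, MK6240, PI2620) and to study participation and procedures. The assessment is to be made "based on temporal relationship and clinical judgment", and the result is graded in the listed categories and entered in the CRF.

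- ***Definitely Related*:** the response to "withdrawal of the study intervention (dechallenge) should be clinically plausible". The event must also be definitive in pharmacological or phenomenological terms, "with use of a satisfactory rechallenge procedure if necessary".
- ***Probably Related*:** the event occurs within a reasonable time, is unlikely to have another cause, and "follows a clinically reasonable response on withdrawal (dechallenge"). For rechallenge the entry adds: "Rechallenge information is not required to fulfill this definition". It has no matching sentence for dechallenge.
- ***Possibly Related*:** for events with some evidence of causation where other factors may have played a part. Such an event may be provisional: "it can be flagged as requiring more information and later be upgraded to" either of the two higher grades.

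The Synopsis (Section 1.1) describes a "Non-randomized, natural history, non-treatment study" and enters N/A for the study intervention. Under Sections 7.3.1.2 and 7.4.2, each participant has one amyloid and one tau scan every two years, and an optional lumbar puncture on the same two-year cycle.

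**The concern.** Dechallenge means stopping an ongoing exposure and watching whether the event abates. That suits a drug taken repeatedly. Here each exposure is over once the injection or puncture is done, usually before the event appears, so nothing remains to be stopped. A site that applies the scale as written must treat the condition as unmet, waive it without authority, or stretch it to mean that the event resolved. The protocol does not say which.

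The protocol supplies a test case. Section 2.3.1.1.3, on lumbar puncture, warns: "Less commonly, a persistent low-pressure headache may develop, probably due to leakage of CSF". This is a recognised procedural event with a known mechanism, and the scale should place it without difficulty. If about 65 sites place it differently, relatedness tabulated across sites will partly reflect how each site read the definition.

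**Working it through.** No figure is stated on this point and none needs recomputing. The check sets the definitions beside the exposures.

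1. **Do the definitions govern?** Yes. The lead-in to Section 7.5.5.2 gives a general basis (timing and judgment), but the next sentence says certainty is graded using the listed categories. Their conditions are therefore rules for the CRF entry.

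2. **Is dechallenge a condition of *Probably Related*?** Yes. It is the last item in a list joined by 'and'. The entry waives rechallenge explicitly and is silent on dechallenge, so the natural reading is that dechallenge is not waived. There is no not-applicable provision.

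3. **Is it a condition of *Definitely Related*?** Less clearly. The verb is 'should', the standard is plausibility, and rechallenge applies only if necessary. The firm 'must' in that grade attaches to the event being definitive. An assessor could find this grade met with nothing to withdraw, or could find it unmet.

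4. **Can the exposures be withdrawn?** No. Repeating the scan or puncture about two years later does not change this. Omitting the next one says nothing about an acute event that followed the previous one.

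5. **Apply this to a post-puncture headache with clear timing and no other explanation.**
   - *Probably Related*: fails on a literal reading, because there is no response to withdrawal.
   - *Definitely Related*: may be met or not, depending on the reader.
   - *Possibly Related*: available, but worded for events with competing explanations, which this case lacks.

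   A literal reader may thus find the highest grade open and the one below it closed, which an ordered scale should not allow.

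6. **Compare with the rest of the section.** The upgrade sentence under *Possibly Related* shows that both higher grades are meant to be reachable. The dechallenge condition obstructs one and clouds the other.

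7. **Does any action depend on the grade?** Sections 7.5.1 and 7.5.3 have all adverse events documented whatever their relationship. Section 7.5.4 has serious events within 24 hours of a tracer reported whatever the investigator thinks of causation, and later serious events reported whether or not related to procedures. No rule turns on reaching either of the top two grades.

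**The case against.** The strongest reply is that the section contains its own remedy. Assessment rests on timing and clinical judgment, *Definitely Related* uses soft language, upgrades are foreseen, and an assessor could treat resolution after exposure as a reasonable response. Parts of the scale are already adapted to this study: *Unlikely Related* mentions the PET tracer product. The study manual, which is not at hand, may also explain how dechallenge applies.

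Much of this stands. A reader might infer that no tracer or procedure event can be graded above *Possibly Related*. The text does not support that, given the softer wording of *Definitely Related*, the stated basis and the upgrade sentence. A reader might also infer that the wording changes which events reach the tracer suppliers or the safety board. That is not supported either. Supplier reporting in Section 7.5.4 sets no grade threshold, *Possibly Related* is itself a related grade, and Section 9.5 has the board review serious event reports without a relatedness filter.

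The reply does not cure *Probably Related*. General reliance on judgment does not cancel a specific listed condition. The protocol nowhere equates resolution with dechallenge. The upgrade sentence reveals the conflict and does not resolve it. A manual could help, but the protocol's own definition would still say otherwise.

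**Conclusion.** The point holds as a wording fault with limited consequences. Read literally, Section 7.5.5.2 closes *Probably Related* to discrete tracer injections and one-off procedures, leaves *Definitely Related* ambiguous, and conflicts with its own basis for grading and its upgrade sentence. Clear-cut tracer or procedural events may be graded inconsistently or too low.

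The harm is confined to the accuracy and between-site consistency of recorded relatedness. No adverse event is lost and no report is suppressed. The size cannot be given in numbers: the protocol states no rate for such events, and counts of scheduled scans or punctures would measure exposure, not misgraded events. For products, the point reaches only the three tracers that the scale names.

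The conclusion assumes that sites apply the definitions as printed and that no manual overrides them. It merits correction because a stated rule misfits the exposures and is cheap to change.

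**What to change.** In Section 7.5.5.2:

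- Under *Definitely Related* and *Probably Related*, remove the dechallenge and rechallenge conditions, or mark them not applicable, for single tracer administrations and study procedures. The remaining criteria are timing, clinical plausibility and absence of another explanation.
- Replace 'study intervention' throughout the scale with 'PET tracer or study procedure', so that it names what participants actually receive.

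The cost is a wording amendment and a matching update to the CRF completion guidance. No new data, visits or procedures are needed.
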